Amendment 06	07-Jul-2016	
Changed top dose to be studied from 16 mg QD to 8 mg QD. Initiation of the 8 mg dose group will only begin following DMC review of safety and laboratory data from the Day 28 study visit for at least 10% of total planned subjects. Changes were made to some exclusion criteria to minimize subject risk. Guidance around the use of CYP3A4 inhibitors and inducers has been further clarified. The statistical sections and sample size calculations have been updated to correspond to these changes.
 
PK sampling windows were expanded; changed requirements for contraception to be the use of one highly effective method of contraception or one less effective method of contraception; added statement to Appendix 1 that local laws and regulations may require use of alternative and/or additional contraception methods; clarified genotyping testing; provided further clarifications to assist with study implementation; updated text per new BMS protocol model document template; corrected typographical errors.

Administrative Letter 02	08-Apr-2016	Changed unit of measure on Exclusion Criteria 3c to Hemoglobin < 9 g/dL.
Administrative Letter 01	25-Feb-2016	Specified that procedures performed as part of standard of care may be used as screening data for the study. Deleted supplies to aid in keeping the study medication cold. Corrected visit numbering in the Time and Events table for Part 2.
Original Protocol	19-Nov-2015	Not applicable

SYNOPSIS

Clinical Protocol CV006004

Protocol Title: A Phase 2, Placebo Controlled, Randomized, Double-Blind, Parallel-Arm Study to Evaluate Efficacy and Safety of BMS-986141 For the Prevention of Recurrent Brain Infarction in Subjects receiving acetylsalicylic acid (ASA) following Acute Ischemic Stroke or Transient Ischemic Attack

Investigational Product(s), Dose and Mode of Administration, Duration of Treatment with Investigational Product(s): Each subject will be administered BMS-986141 or matching placebo once daily (QD) in a blinded fashion with open label acetylsalicylic acid (ASA) at a dose of 75 to 162 mg/day in the following treatment groups. ASA is a non-investigational product in this study.

Treatment A: Subjects will receive matching placebo (to BMS-986141) QD for up to 28 days in Part 1 of the Study or up to 90 days in Part 2 of the Study

Treatment B: Subjects will receive BMS-986141 0.8 mg QD for up to 28 days in Part 1 of the Study or up to 90 days in Part 2 of the Study

Treatment C: Subjects will receive BMS-986141 4.8 mg QD for up to 28 days in Part 1 of the Study or up to 90 days in Part 2 of the Study

Treatment D: Subjects will receive BMS-986141 8 mg QD for up to 28 days in Part 1 of the Study or up to 90 days in Part 2 of the Study

Study Phase: 2

Research Hypothesis: BMS-986141 is effective in reducing the recurrence of stroke in subjects with recent transient ischemic attack (TIA) or stroke.

Objectives:

Primary Objective:

To determine the dose-response relationship of BMS-986141 on the recurrence of brain infarction at 28 days as assessed by a composite of symptomatic ischemic stroke and unrecognized brain infarction as assessed by MRI in subjects with ischemic stroke or TIA treated with ASA.

Secondary Efficacy Objectives:

- To assess the effect of BMS-986141 on the occurrence of major adverse cardiovascular events (MACE, including all stroke, myocardial infarction, and CV death) by Day 90
- To assess the effect of BMS-986141 on the occurrence of the composite of ischemic stroke, myocardial infarction, and CV death by Day 90
- To assess the effect of BMS-986141 on incidence of symptomatic recurrent stroke up to 28 days of treatment
- To assess the effect of BMS-986141 on the occurrence of the composite of unrecognized brain infarction assessed by MRI at Day 28 and MACE by Day 90

Safety Objectives:

- To assess the effect of BMS-986141 on the composite of Major and Clinically Relevant Non-Major (CRNM) Bleeding
- To assess the effect of BMS-986141 on all reported bleeding
- To evaluate safety and tolerability of BMS-986141

Study Design: This is a randomized, double-blind, placebo-controlled, parallel-arm, study to evaluate the efficacy and safety of BMS-986141 in addition to ASA in subjects following acute ischemic stroke or transient ischemic

[figure not shown]
attack (TIA). Eligible subjects will be randomized within 48 hours of the time they were last seen normal prior to acute ischemic stroke/TIA and must have a baseline study-specific MRI no later than 24 hours after randomization.

The study will be conducted in two parts. Subjects in both parts of the study will be randomly assigned to one of three different doses of BMS-986141 or matching placebo and will continue on the assigned dose for the duration of the treatment period. Initially randomization will be limited to the two lower doses of BMS-986141 or placebo. Randomization to the highest dose of BMS-986141 will only be initiated after DMC review of safety and laboratory data from the Day 28 study visit for at least 10% of the planned total subjects. In Part 1 of the study, the treatment period will be 28 days. Part 2 of the study will only be initiated after regulatory review of reports from 90-day nonclinical toxicology studies. The treatment period in Part 2 will be 90 days.

[figure not shown]
The Primary efficacy endpoint will be assessed at 28 days after the initial dose in all subjects. Additional objectives will be assessed at 28 or 90 days.

Study Schematic:

CV006-004 Study Schematic - Part 1 of study

CV006-004 Study Schematic - Part 2 of study

Study Population: Male and female subjects, ≥ 18 years of age who meet the inclusion and exclusion criteria for the study as determined by medical history, physical examination, 12-lead electrocardiogram (ECG), and clinical laboratory evaluations will be eligible to participate in the study.

Potentially eligible subjects:

- Must have had an acute ischemic stroke (National Institutes of Health Stroke Scale (NIHSS) ≤ 7) or high risk TIA (ABCD2 score ≥ 4 or motor or speech symptoms; or atherosclerotic stenosis that could account for clinical presentation for which there is not a plan for revascularization therapy)
- Must have had head Computed Tomography (CT) or MRI ruling out hemorrhage or other pathology
- Randomization occurring within 48 hours after onset of symptoms; if symptoms are first present on awakening, onset should be considered as time last seen normal
- Must not have clinical evidence or any history of atrial fibrillation (other than transient AF related to cardiac surgery), severe left ventricular systolic dysfunction, left ventricular thrombus, or other high-risk cardioembolic source deemed the likely cause of brain ischemia
- Must be able to have a study-specific MRI no later than 24 hours after randomization

Study Drug: Includes both Investigational [Medicinal] Products (IP/IMP) and Non-investigational [Medicinal] Products (Non-IP/Non-IMP) as listed:

Study Drug for BMS-986141		
Medication	Potency	IP/Non-IP
BMS-986141	0.8 mg	IP
BMS-986141	4 mg	IP
Placebo (matching to BMS-986141)	0 mg	IP
Acetylsalicylic acid	75–162 mg	Non-IP

Study Assessments:

Safety: The main safety outcome of the study is bleeding. Subjects with bleeding or suspected bleeding will undergo confirmatory laboratory or other testing (ultrasound [US], CT, MRI, etc.) and an (S)AE CRF must be completed. All

clinically overt bleeding events that lead to medical treatment or evaluation, or discontinuation of study medication must be submitted for adjudication. Bleeding will be adjudicated by a blinded Clinical Events Adjudication Committee (CEC) according to definitions adapted from the International Society on Thrombosis and Hemostasis (ISTH). Bleeding will be classified as Major Bleeding, Clinically Relevant Non-Major (CRNM) Bleeding, or Minor Bleeding.

An independent Data Monitoring Committee (DMC), separate from the CEC, will monitor the safety of all subjects during the study and give recommendations to the Study Executive Committee. At the beginning of the study, subjects will be randomized to placebo, 0.8 or 4.8 mg of BMS-986141, with no subjects being randomized to the 8 mg dose. The DMC will review safety data when at least 10% of the total planned subjects for the study have completed their scheduled Day 28 visit and clinical laboratory results and other safety data from those subjects are available. Data to be included in that review will be specified in the DMC charter. As a result of this review, the DMC can recommend expansion of the randomization to all 4 study arms, additional experience on placebo and the 2 lower doses, or other modifications as necessary to ensure subject safety.

Efficacy: The primary efficacy endpoint of the study is the incidence of a composite of symptomatic ischemic stroke by Day 28 and unrecognized brain infarction assessed by MRI at Day 28. Additional Secondary Efficacy Endpoints include Major Adverse Cardiovascular Events, including symptomatic stroke, myocardial infarction, and cardiovascular death. Symptomatic efficacy events will be adjudicated by the CEC. Unrecognized brain infarction will be adjudicated by a blinded imaging adjudication committee (IAC) based on comparisons of MRI at baseline and Day 28.

Statistical Considerations:

Sample Size:

The primary efficacy endpoint of the study is the incidence of a composite of symptomatic ischemic stroke by Day 28 and unrecognized brain infarction at Day 28. Initially, randomization will be limited to the two lower doses of BMS-986141 (0.8 mg or 4.8 mg) or placebo in a 1:1:1 ratio until after DMC review of safety and laboratory data from the Day 28 study visit for at least 10% of planned total subjects (approximately 132 subjects). If the DMC recommends proceeding to inclusion of the highest dose (8 mg), subsequent randomization will be in a 1:1:1:1 ratio. Based on the staggered randomization and with a total of 1240 evaluable subjects, there is at least 80% power to demonstrate a dose-response relationship assessed by MCP-Mod method (see below), with Emax and logistic models included as candidate models, and using a 1-sided type I error of 15%. This assumes a true incidence for placebo of 14%, a maximum relative risk reduction of 30% for BMS 986141 8mg compared to placebo, and reductions of 75% and 90% of the maximum reduction for the 0.8 and 4.8 mg doses, respectively. To account for about 5% of subjects without post-randomization data, a total of 1312 subjects will be randomized.

Endpoints:

Primary efficacy endpoint

The primary efficacy endpoint of the study is the incidence of a composite of symptomatic ischemic stroke by Day 28 and unrecognized brain infarction assessed by MRI at Day 28.

Additional efficacy endpoints

Secondary endpoints:

- The incidence of major adverse cardiovascular events (MACE) by Day 90, defined as a composite of all adjudicated stroke, myocardial infarction, or CV death
- The incidence of the composite of adjudicated ischemic stroke, myocardial infarction, and CV death by Day 90
- The incidence of adjudicated symptomatic stroke (including fatal and non-fatal) by Day 28
- The incidence of the composite of unrecognized brain infarction assessed by MRI at Day 28 and MACE by Day 90

Primary safety endpoint

The primary safety endpoint will be incidence of a composite of adjudicated major bleeding and adjudicated CRNM bleeding during the treatment period.

Additional safety endpoints

- Additional safety endpoints include the incidence of adjudicated major bleeding events, all bleeding events, intracranial hemorrhage events, as well as the incidence of AEs and markedly abnormal standard clinical laboratory test results.

Analyses:

Adjudicated results will be the basis for the primary and secondary analyses.

Primary Efficacy Endpoint Analysis:

- To demonstrate the dose-response relationship between BMS-986141 treatment (including placebo) and primary endpoint, the primary analysis will be based on an MCP-Mod analysis. This analysis tests for a dose-response relationship, allowing for uncertainty in the dose-response relationship through inclusion of contrasts from pre-specified candidate models to assess dose-response. Fitted estimates for the incidence of the primary endpoint will be calculated in each of the treatment groups using a weighted model-averaging method
- The incidence of the composite of adjudicated symptomatic recurrent ischemic stroke by Day 28 and unrecognized brain infarction at Day 28 will also be summarized by treatment. Point estimates and 95% CIs for event rates will be presented by treatment, together with point estimates and 95% CIs for the relative risk reduction between each BMS-986141 arm and placebo
- A single categorical variable based on study change points (length of treatment [28 or 90 days] and randomization phase [randomized prior to or after DMC safety interim analysis decision]) will be included as a covariate

Secondary Efficacy Endpoint Analyses

- Similar analysis methods will be used for the secondary endpoint incidence of MACE as for the primary endpoint
- A sequential testing approach will be used for the primary and MACE endpoints. Dose-response relationship for the primary endpoint will be tested first using a one-sided 0.15 type I error; if the p-value for this comparison is < 0.15 , then the dose-response relationship for the same endpoint will be tested using a one-sided 0.025 type I error. If the p-value for this comparison is < 0.025 , then the dose-response relationship for the MACE endpoint will be tested using a one-sided 0.025 type I error
- Other secondary endpoints will use similar analysis methods as the primary and secondary endpoint of MACE

Safety analysis:

- For safety analyses, separate summaries taking into account length of treatment (28 or 90 days) and randomization phase (randomized prior to or after DMC safety interim analysis decision) will be provided
- The incidences of the composite of major bleeding and clinically relevant non-major (CRNM) bleeding, all bleeding events (including major bleeding, clinically relevant non-major bleeding and minor bleeding), and intracranial hemorrhage during the treatment period will be summarized by treatment. Point estimates and 95% CIs for event rates of each of above safety endpoint will be presented by treatment, together with point estimates and 95% CIs for the difference of event rates between each BMS-986141 arm and placebo. A single categorical variable based on study change points (length of treatment [28 or 90 days] and randomization phase [randomized prior to or after DMC safety interim analysis decision]) will be included as a stratum in the calculation of the CIs
- All other safety endpoints will be summarized descriptively by treatment

TABLE OF CONTENTS

TITLE PAGE	1
DOCUMENT HISTORY	3
SYNOPSIS.....	4
TABLE OF CONTENTS.....	9
1 INTRODUCTION AND STUDY RATIONALE	12
1.1 Study Rationale.....	12
1.2 Research Hypothesis.....	13
1.3 Objectives(s)	13
1.3.1 Primary Objectives	13
1.3.2 Secondary Objectives.....	13
1.3.3 Safety Objectives.....	13
1.3.4 Exploratory objectives	14
1.4 Product Development Background.....	14
1.4.1 Clinical Pharmacology and Safety	14
1.4.1.1 Pharmacokinetics of BMS-986141	15
1.4.1.2 Dose Selection.....	15
1.5 Overall Risk/Benefit Assessment	15
2 ETHICAL CONSIDERATIONS.....	16
2.1 Good Clinical Practice	16
2.2 Institutional Review Board/Independent Ethics Committee.....	16
2.3 Informed Consent.....	17
3 INVESTIGATIONAL PLAN.....	18
3.1 Study Design and Duration.....	18
3.2 Post Study Access to Therapy.....	21
3.3 Study Population.....	21
3.3.1 Inclusion Criteria.....	21
3.3.2 Exclusion Criteria.....	23
3.4 Concomitant Treatments.....	25
3.4.1 Prohibited and/or Restricted Treatments.....	25
3.4.2 Other Restrictions and Precautions.....	26
3.4.3 MRI Contraindications	26
3.5 Discontinuation of Subjects following any Treatment with Study Drug.....	27
3.6 Post Study Drug Study Follow up	28
3.6.1 Withdrawal of Consent	28
3.6.2 Lost to Follow-Up.....	29
4 STUDY DRUG.....	30
4.1 Investigational Product	31
4.2 Non-investigational Product	31
4.3 Storage of Study Drug	31
4.4 Method of Assigning Subject Identification.....	31
4.5 Selection and Timing of Dose for Each Subject.....	32
4.5.1 Dose Modifications	32
4.6 Blinding/Unblinding	33
4.7 Treatment Compliance.....	34

4.8 Destruction or Return of Investigational Product	34

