8 STATISTICAL CONSIDERATIONS

8.1 Sample Size Determination

The primary efficacy endpoint of the study is the incidence of a composite of symptomatic ischemic stroke by Day 28 and unrecognized brain infarction at Day 28. Sample size calculations were performed for detecting a dose-response effect with the MCP-MOD methodology using simulations with the DoseFinding package in R¹⁴. Simulations of 1000 clinical trials were performed, assuming a true incidence for placebo of 14%, a maximum relative risk reduction of 30% for BMS-986141 8 mg relative to placebo, and relative reductions of 75% and 90% of the maximum for the 0.8 and 4.8 mg doses, respectively. Candidate models included an Emax model and a logistic model.

Initially, randomization will be limited to the two lower doses of BMS-986141 (0.8 mg or 4.8 mg) or placebo in a 1:1:1 ratio until after DMC review of safety and laboratory data from the Day 28 study visit for at least 10% of planned total subjects (approximately 132 subjects). If the DMC recommends proceeding to inclusion of the highest dose (8 mg), subsequent randomization will be in a 1:1:1:1 ratio. Based on the staggered randomization as shown in Table 8.1-1 and the assumptions above, the study will have at least 80% power to demonstrate a dose-response relationship, using a 1-sided type I error rate of 15%. A total sample size of 1312 randomized subjects accounts for about 5% of subjects without post-randomization data.

Table 8.1-1: Randomization Targets^a

	Placebo	0.8 mg	4.8 mg	8 mg
Prior to interim safety review by DMC: 132 subjects (1:1:1 randomization ratio)	44	44	44	0
Additional subjects randomized while interim safety tables are being generated and reviewed by the DMC (not included in DMC safety interim analysis): 100 subjects (1:1:1 randomization ratio)	34	33	33	0
After interim safety review by DMC: 1081 subjects	270	270	270	270
Total: 1312 subjects	348	347	347	270

^a Numbers shown for each treatment group are estimates based on randomization ratio. Actual numbers could be slightly different based on randomization block size.

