4 ENDPOINTS

4.1 Primary Efficacy Endpoint

The primary efficacy endpoint of the study is the incidence of a composite of symptomatic ischemic stroke by Day 28 and unrecognized brain infarction assessed by MRI at Day 28. Each of these will be assessed by an adjudication committee. If a subject experiences any of these events, the subject will be counted as having experienced a composite event in the analysis.

In the event that one, but not both of the components of the primary endpoint cannot be ascertained, then the remaining component will be evaluated. In this case, if the remaining component is counted as an event, the composite event will be considered as having occurred. If, however, the remaining component is not counted as an event, or if both of the components of the primary endpoint cannot be ascertained, the resulting primary endpoint will be considered as missing.

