5 SAMPLE SIZE AND POWER

The primary efficacy endpoint of the study is the incidence of a composite of symptomatic ischemic stroke by Day 28 and unrecognized brain infarction at Day 28. Sample size calculations were performed for detecting a dose-response effect with the MCP-MOD methodology using simulations with the DoseFinding package in R⁴. Simulations of 1000 clinical trials were performed, assuming a true incidence for placebo of 14%, a maximum relative risk reduction of 30% for BMS-986141 8 mg relative to placebo, and relative reductions of 75% and 90% of the maximum for the 0.8 and 4.8 mg doses, respectively. Candidate models included an Emax model and a logistic model.

Initially, randomization will be limited to the two lower doses of BMS-986141 (0.8 mg or 4.8 mg) or placebo in a 1:1:1 ratio until after the DMC review of safety and laboratory data from the Day 28 study visit for at least 10% of planned total subjects (approximately 132 subjects). If the DMC recommends proceeding to inclusion of the highest dose (8 mg), subsequent randomization will be in a 1:1:1:1 ratio. Based on the staggered randomization as shown in in the table below and the assumptions above, the study will have at least 80% power to demonstrate a dose-response relationship, using a 1-sided type I error rate of 15%. A total sample size of 1312 randomized subjects accounts for about 5% of subjects without post-randomization data.

Table 5-1: Randomization Targets

	Placebo	0.8 mg	4.8 mg	8 mg
Prior to interim safety review by the DMC: 132 subjects (1:1:1 randomization ratio)	44	44	44	0
Additional subjects randomized while interim safety reports are being generated and reviewed by the DMC (not included in the DMC safety interim analysis): 100	34	33	33	0

Table 5-1: Randomization Targets

	Placebo	0.8 mg	4.8 mg	8 mg
subjects (1:1:1 randomization ratio)				
After interim safety review by DMC: 1081 subjects	270	270	270	270
Total: 1312 subjects	348	347	347	270

Note: Numbers shown for each treatment group are estimates based on randomization ratio. Actual numbers could be slightly different based on randomization block size and rate of enrollment.

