7.1.2 General Methods for Efficacy Analyses

Generalized Multiple Comparison Modelling (gMCP-Mod)

To demonstrate the dose-response relationship between BMS-986141 treatment (including placebo) and the primary endpoint, the primary analysis will be based on a generalized Multiple Comparisons and Modeling (gMCP-Mod) analysis⁵⁶. This analysis tests for a dose-response relationship, allowing for uncertainty in the dose-response relationship through inclusion of contrasts from multiple pre-specified candidate models to assess dose-response. If a dose-response relationship exists, then fitted estimates for the incidence of the primary endpoint will be calculated in each of the treatment groups using the selected dose-response models.

The gMCP-Mod procedure extends the MCP-Mod methodology to non-continuous endpoints. This is accomplished by decoupling the dose-response model from the expected response through the use of an ANOVA style parameterization of the dose-response parameter. For the binary endpoint used in this study, a logistic regression of the event proportion at each dose level will be used, following adjustment for study time period (1A, 2A, 2B) via the inclusion of an additive covariate. After this first step, the mean parameter estimates from the logistic model and the corresponding covariance matrix, both of which are on the logit scale, will then be used during the rest of the gMCP-Mod procedure. Point estimates from the selected models will be displayed on the proportion scale in all statistical outputs.

Candidate Models and Multiple Testing Procedure

There are two candidate models that will be considered for the primary analysis. These are an Emax model and a logistic model, where dose-response will be tested using dose levels of 0 (placebo), 1, 2, and 2.3 (corresponding to 0.8 mg, 4.8 mg, and 8 mg)⁷.

The MCP-Mod procedure requires certain parameter estimates be pre-specified for the candidate models based on available information in order to derive optimum contrast coefficients for testing the null hypothesis: that a dose-response does not exist in any of the candidate models. It

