is through testing this hypothesis that the model which best describes the dose-response relationship will be identified⁸. The parameters used to determine the contrast for testing will assume a placebo event rate of 14% and maximum risk reduction of 4.2%. For the Emax model, the required parameter estimates used will be 1.0 for the dose corresponding to half of the maximum effect and 1.0 for a “Hill” parameter that determines the steepness of the model at the dose of half effect. For the logistic model, these parameter estimates used will be 1.0 for the dose corresponding to half effect and 0.1 for the parameter that determines the steepness of the curve. These pre-specified parameter estimates will remain fixed through the contrast testing portion of the gMCP-Mod procedure in order to preserve the type I error.

The gMCP-Mod procedure for non-continuous endpoints diverges from the original MCP-Mod procedure in the calculation of the optimum contrast coefficients. The gMCP-Mod methods that will be used to calculate the optimum contrast coefficients require the pre-specified model parameters from above along with the covariance matrix from the logistic regression in the first step. In practice, since the covariance matrix in the first step is based on actual data, the optimum contrast coefficients are recalculated when the actual data become available. The parameter estimates for the candidate models, however, will remain fixed.

These optimal contrast coefficients follow the form given below, and will be recalculated as described using the DoseFinding package in R once the actual data are available.

$$c_m^{opt} \propto S^{-1} \left(\mu_m - \frac{\mu_m' S^{-1} \mathbf{1}}{\mathbf{1}' S^{-1} \mathbf{1}} \right)$$

Where μ_m is the event rate on the logit scale based on the corresponding candidate model m ($m=1, 2$) at the specified dose levels, and S corresponds to the covariance matrix from the logistic regression on the actual data in the first step.

In order to demonstrate a dose-response relationship, the following global hypothesis will be tested:

$$H_0: c_m^{opt} \mu \geq 0 \text{ for all } m \in \{1, 2\}$$

$$H_1: c_m^{opt} \mu < 0 \text{ for at least one } m \in \{1, 2\}$$

where μ is the true event rate on the logit scale at the specified dose levels.

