For each candidate model ($m=1, 2$), the contrast test statistic (z_m) is calculated as standardized linear combinations of the estimated event rate on the logit scale from the logistic regression using the optimal contrast coefficients associated with that candidate model.

A multiplicity-adjusted critical value will be determined from the joint multivariate normal distribution of the contrast test statistics at the overall one-sided alpha level of 0.15. If either test statistic that exceeds this critical value, a dose-response relationship will be demonstrated.

Modelling and Estimation

The model for estimation will be selected from among the two candidate models with a contrast test statistic that is greater than or equal to the multiplicity-adjusted critical value. If both

candidate models have such contrast test statistics, then both models will be employed using a weighted averaging technique based on their relative Bayesian Information Criteria (BIC), for the purposes of estimation. If neither candidate model has a contrast test statistic that is greater than or equal to the multiplicity-adjusted critical value, then the analysis will end, indicating that a dose-response relationship cannot be established.

In this manner, the point estimates for the means will be generated from the selected model as described in the efficacy analyses in [Section 7.5](#).

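### The plan states at least 80% power at 1240 evaluable subjects, but the test the SAP specifies has about 76% there and about 77.4% even at 1312.

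*Protocol*

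**What the plan says.** The Synopsis of the Protocol (Sample Size) states that "with a total of 1240 evaluable subjects, there is at least 80% power to demonstrate a dose-response relationship assessed by MCP-Mod method", "using a 1-sided type I error of 15" percent, and inflates 1240 to 1312 randomized. Protocol 8.1 gives the same effect assumptions, reports 1000 simulated trials run with the DoseFinding package, and adds: "A total sample size of 1312 randomized subjects accounts for about 5% of subjects without post-randomization data". SAP 5 carries the claim forward: "the study will have at least 80% power to demonstrate a dose-response relationship, using a 1-sided type I error rate of 15" percent. SAP 5 does not name 1240; like Protocol 8.1, it ties the 80% to the randomization table that totals 1312.

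SAP 7.1.2 defines the test. The arm estimates come from a logistic regression with an additive study-period covariate (1A, 2A, 2B). These estimates and their covariance matrix, "both of which are on the logit scale, will then be used during the rest of the gMCP-Mod procedure". On the contrasts, "the optimum contrast coefficients are recalculated when the actual data become available". On the threshold: "A multiplicity-adjusted critical value will be determined from the joint multivariate normal distribution" of the two test statistics, at one-sided 0.15.

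SAP 4.1 limits how many subjects count. When one component cannot be ascertained and "the remaining component is not counted as an event, or if both of the components of the primary endpoint cannot be ascertained", the primary endpoint is set to missing.

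**The concern.** A reader takes the 80% as the probability that the planned primary test will detect the assumed 30% maximum reduction. All the inputs needed to check it are in the documents, so the figure should be recoverable. Under the procedure in SAP 7.1.2 it is not, at 1240 or at 1312. The larger size is also unlikely to be reached, because SAP 4.1 removes subjects who have an unascertained component and no event on the other.

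What is at stake is the stated risk of a false negative in a dose-response study. The validity of the test is not in question.

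**Working it through.** **Inputs from the documents**
- Event rates (Synopsis, Protocol 8.1, SAP 5): placebo 14%. The maximum reduction is 0.30 × 14 = 4.2 points. The arms are then 8 mg 14 − 4.2 = 9.8%, 0.8 mg 14 − 0.75 × 4.2 = 10.85%, and 4.8 mg 14 − 0.90 × 4.2 = 10.22%.
- Allocation (Protocol Table 8.1-1, SAP Table 5-1): 348/347/347/270 at 1312. Scaled by 1240/1312, this is 329/328/328/255.
- Dose scores 0, 1, 2, 2.3. Candidates: Emax (half-effect 1.0, Hill 1.0) and logistic (half-effect 1.0, steepness 0.1) (SAP 7.1.2).
- One-sided alpha 0.15.
- Inflation check: 1240/0.95 = 1306, consistent with 1312.

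**Step 1: a ceiling that can be checked by hand.** Take the best possible single logit contrast, built from the true rates, with no multiplicity penalty. Its noncentrality is √Σwᵢ(ℓᵢ − ℓ̄)², where wᵢ = nᵢpᵢ(1 − pᵢ), ℓᵢ is the logit of pᵢ, and ℓ̄ is the w-weighted mean. At 1240:

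| Arm | w | logit | w(ℓ − ℓ̄)² |
|---|---|---|---|
| Placebo | 39.61 | −1.8153 | 2.184 |
| 0.8 mg | 31.73 | −2.1062 | 0.100 |
| 4.8 mg | 30.10 | −2.1730 | 0.455 |
| 8 mg | 22.54 | −2.2196 | 0.648 |

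Here ℓ̄ = −2.0501, the last column sums to 3.386, and the noncentrality is 1.840. Power = Φ(1.840 − 1.036) = 78.9%. So asymptotically no logit-scale contrast test that holds 15% reaches 80% at 1240. At 1312 the noncentrality is 1.893 and the same ceiling is Φ(1.893 − 1.036) = 80.4%, before any cost for using two candidate shapes.

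**Step 2: the SAP procedure, simulated.** In each trial:
1. Draw binomial counts by arm.
2. Compute the logits and their inverse-information covariance S.
3. Form c ∝ S⁻¹(μ − (μ′S⁻¹1)/(1′S⁻¹1)) for each candidate.
4. Compute z = c′logit/√(c′Sc).
5. Compare the larger statistic, signed so that benefit is positive, with the bivariate-normal critical value at 0.15 (correlation 0.97, critical value 1.128–1.131).

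Ranges below cover candidate shapes defined on the probability or the logit scale, and repeat runs.

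| Version | 1240 | 1312 |
|---|---|---|
| SAP procedure, 400,000 trials (SE 0.07 points) | 75.7–76.0% | 77.3–77.5% |
| SAP procedure with 1A/2A/2B covariate, 60,000 trials | 75.4–75.9% | 76.8–77.3% |
| Contrasts fixed from the assumed rates | 77.9–78.2% | 79.4–79.8% |

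The split of Phase A between 1A and 2A is not given; a 1A share of 30–70% was assumed.

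**Step 3: what would give 80%**
- *More subjects, SAP procedure:* 79.2–79.4% at 1399, 79.8–80.2% at 1440, 80.3–80.5% at 1459. About 1440–1460 evaluable are needed.
- *A larger effect, SAP procedure at 1240:* a maximum reduction of 32% gives 79.6–79.7%, 32.5% gives 80.4–80.8%, and 33% gives 81.4–81.5%. At 1312 about 31.5% suffices.
- *An unadjusted critical value (1.036) at 1240:* fixed contrasts give 80.6–80.8%, but type I error rises to about 17% (asymptotic) or 18% (simulated), against SAP 7.1.2. With the SAP's recalculated contrasts it gives only 78.7%.
- *A planning formula that gives every arm the placebo variance (14%):* 80.3–80.6% at 1240 with the adjusted critical value. Simulating the plan's actual rates with those contrasts gives 77.7–77.9%.

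**Step 4: more missing endpoints.** If 10% lacked the endpoint (an assumption; about 1180 evaluable), power would be 74.4–74.5%.

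**Step 5: simulation noise.** The probability that 1000 simulated trials show 800 or more successes is 0.001 if true power is 76%, 0.026 at 77.4%, 0.07–0.09 at 78%, and 0.36–0.43 at 79.5–79.7%.

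**The case against.** The strongest reply is that the 80% was a reasonable planning figure. The Protocol describes MCP-Mod without saying that contrasts are recalculated from the data; that enters in SAP 7.1.2. Against a fixed-contrast calculation the gap is only about 2 points at 1240 and under 1 point at 1312. A run of 1000 trials has a standard error of about 1.3 points, so at 1312 a result of 80% would be unremarkable. A planning calculation using the 14% variance in every arm reproduces at least 80% at 1240 without dropping the multiplicity adjustment. Finally, part of the gap between 76% and 78% is calibration: under the null at 1240 the SAP version rejects 14.2–14.3%, against 15.6–15.8% with fixed contrasts.

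Much of this stands. It shows how the figure could have arisen, and it is why no slip in the Protocol 8.1 run is alleged. It does not make the statement true of the planned test. The equal-variance route contradicts the plan's own assumed rates in the active arms, and its apparent 80% disappears when those rates are simulated. Noise in the planning run explains a reported number but does not raise the power. Fixed contrasts still fall short of 80% at both sizes. The Synopsis names 1240 evaluable explicitly, and SAP 5 repeats the 80% in the same document that specifies recalculated contrasts.

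**Conclusion.** The concern holds, as a minor point. Under the documents' own assumptions, the primary test in SAP 7.1.2 has about 76% power at 1240 evaluable subjects and about 77.4% at 1312, roughly 4 and 2.5 points below the stated minimum. About 2 points of the shortfall come from recalculating the contrasts, part of which is slight conservatism under the null.

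The result rests on the stated rates, allocation, dose scores and candidate parameters, and changes little with the period covariate or with the scale on which the candidate shapes are defined. The method behind the sponsor's planning figure cannot be identified, because Protocol 8.1 does not give its scale, contrast handling or covariate use. Type I error, the analysis and the decision rule are unaffected.

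**What to change.** Keep the sample size. In Protocol 8.1 and SAP 5, state the N, scale, candidate parameters, variance assumption and contrast handling used in the 1000 planning simulations. Rerun the SAP 7.1.2 procedure at 1240 evaluable with at least 10,000 trials. Then restate the power in the Synopsis, Protocol 8.1 and SAP 5 as the resulting figure (expected to be about 76%), or say that 80% holds only for a maximum relative reduction of about 32–33%.

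The cost is one simulation rerun, a short description of the method, and one corrected sentence in each of three places. No extra patients are needed, and the analysis does not change. The stated power becomes slightly less favourable.
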